10.2.2.1. Analyses of the Primary Endpoint for the Phase 1 Randomization

Question 1 (Table 10.1): Does a PCST intervention consisting of weekly, live, coach-led sessions improve outcomes at 12 weeks?

Question 1 addresses the primary trial hypothesis. The primary efficacy endpoint, the change in BPI Interference between baseline and 12 weeks, and will be analyzed using a linear mixed effects model.⁶² The linear mixed effects model will include fixed effects of intervention, time, and interactions between intervention and time, taking into account the repeated measures over time and clustering of recruitment sites via random effects. All repeated measures of the BPI Interference scores at baseline and 12 weeks will be included in the model as the dependent variable. The linear mixed effects model is expressed as

$$y_{ijk} = \beta_0 + \beta_1 X_{ij} + \beta_2 I(T_{ijk} = 12) + \beta_3 X_{ij} I(T_{ijk} = 12) + \gamma^T \mathbf{W}_{ij} + \theta_i + \alpha_{ij} + \varepsilon_{ijk},$$

where y_{ijk} is the BPI Interference score for participant ij ($i = 1, 2, \dots, 14$; $j = 1, 2, \dots, n_i$; n_i is number of participants from recruitment site i) at time point k ($k = 1, 2$), X_{ij} is the binary intervention indicator ($X_{ij} = 1$ if PCST; $X_{ij} = 0$ if Usual Care) for participant ij , T_{ijk} is the study weeks for participant ij at time point k ($T_{ij1} = 0$ and $T_{ij2} = 12$), $I(\cdot)$ is an indicator function returning 1 (0) if the event is true (false), \mathbf{W}_{ij} is a vector of baseline measures, including the stratification factors, for participant ij , β 's and γ are regression parameters for the fixed effects, θ_i and α_{ij} are the regression parameters for the random effects for recruitment site i and participant ij , respectively, and ε_{ijk} is the random error for participant ij at time point k . Model diagnostics will be conducted to examine the assumption of normality. If there are potential violation of the assumptions, transformations of the data beginning with a log transformation will be explored. The primary efficacy estimand is the contrast of PCST and Usual Care for the change at the 12-week time point; i.e., β_3 . Differences in changes, their 95% confidence intervals, and p-values will be presented.

Question 2 (Table 10.1): Does a PCST intervention consisting of weekly, live, coach-led sessions for 12 weeks followed by IVR for 12 weeks improve outcomes at 24 weeks?

To answer this question, the aforementioned linear mixed effects model is revised by adding the BPI Interference score at 24 weeks to the dependent variable. The linear mixed effects model is expressed as

$$y_{ijk} = \beta'_0 + \beta'_1 X_{ij} + \beta'_2 I(T_{ijk} = 12) + \beta'_3 I(T_{ijk} = 24) + \beta'_4 X_{ij} I(T_{ijk} = 12) + \beta'_5 X_{ij} I(T_{ijk} = 24) + \gamma'^T \mathbf{W}_{ij} + \theta'_i + \alpha'_{ij} + \varepsilon'_{ijk},$$

where y_{ijk} is the BPI Interference score for participant ij at time point k ($k = 1, 2, 3$) and $T_{ij3} = 24$. The estimand for **Question 2 in Table 10.1** is the contrast of PCST and Usual Care for the change at the 24-week time point; i.e., β'_5 . Differences in changes, their 95% confidence intervals, and p-values will be presented.

Question 3 (Table 10.1): Are the effects of PCST sustained?

To answer this question, the aforementioned linear mixed effects model is revised by adding the BPI Interference score at 36 weeks to the dependent variable. The linear mixed effects model is expressed as

$$y_{ijk} = \beta_0'' + \beta_1'' X_{ij} + \beta_2'' I(T_{ijk} = 12) + \beta_3'' I(T_{ijk} = 24) + \beta_4'' I(T_{ijk} = 36) + \beta_5'' X_{ij} I(T_{ijk} = 12) + \beta_6'' X_{ij} I(T_{ijk} = 24) + \beta_7'' X_{ij} I(T_{ijk} = 36) + \gamma''^T W_{ij} + \eta'' V_{ij} I(T_{ijk} \geq 24) + \delta'' Z_{ij} I(T_{ijk} \geq 24) + \theta_i'' + \alpha_{ij}'' + \varepsilon_{ijk}''$$

where y_{ijk} is the BPI Interference score for participant ij at time point k ($k = 1, 2, 3, 4$), $T_{ij4} = 36$, V_{ij} is the binary buprenorphine eligibility indicator ($V_{ij} = 1$ if buprenorphine eligible; $V_{ij} = 0$ if not buprenorphine eligible), Z_{ij} is the binary buprenorphine indicator ($Z_{ij} = 1$ if initiated buprenorphine; $Z_{ij} = 0$ if declined buprenorphine), and η'' and δ'' are regression parameters for the fixed effects. The estimand for **Question 3** in **Table 10.1** is the contrast of PCST and Usual Care for the change at the 36-week time point; i.e., β_7'' . Differences in changes, their 95% confidence intervals, and p-values will be presented.

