10.2. Statistical Considerations for the Phase 1 Randomization

10.2.1. Sample Size and Power Analysis for the Primary Objective

The primary objective for Phase 1 is to compare changes from baseline to 12 weeks in the BPI Interference scores between the PCST and Usual Care groups. The null hypothesis is that the change in BPI Interference score is the same in the PCST and Usual Care groups.

Table 10.2 depicts the minimum detectable difference between the PCST and Usual Care groups in the change in BPI Interference score, for a power of 90%, a type 1 error of 5%, an attrition rate of 20%, standard deviations of change of 2 and 3, a total number of participants ranging from 480 – 800 (participant numbers per Clinical Center ranging from 60 to 100), intra-class correlation coefficients of 0 and 0.02, and an interim analysis of one look at 50% information time. Details of the interim analysis are described in **Section 10.2.3**. All calculations are based on two-sample t tests. As one example, if the total sample size is 640, the number of participants per Clinical Center is 80, the ICC is 0 (i.e., no clustering effect), and the standard deviation of the change in BPI Interference score is 2, the BPI Interference score for PCST would need to decrease by at least 0.62 points if the change in BPI Interference score for Usual Care were 0 (**Table 10.2, Row #2**). As another example, again using the parameters in **Table 10.2, Row #2**, the change in the BPI Interference score would need to decrease by 1.02 in the PCST group if the score decreased by 0.40 in the Usual Care group.

Table 10.2. Minimum Detectable Differences between the PCST and Usual Care Groups in the Change from Baseline to Week 12 in the BPI Interference Score

Row	Total N	Clinical Center n	ICC	Minimum Detectable Between-Group Difference in Change in BPI Interference Score ¹	
				If SD = 2	If SD = 3
1	800	100	0	0.56	0.83
2	640	80	0	0.62	0.93
3	480	60	0	0.72	1.08
4	800	80	0.02	0.73	1.10
5	640	80	0.02	0.78	1.17
6	480	60	0.02	0.86	1.29

¹Effect sizes determined for a power of 90%, at a type 1 error of 5%, an attrition rate of 20%, standard deviations of change of 2 and 3, and an interim analysis of one look at 50% information time, using two-sample t tests.

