10.2.2. Statistical Analyses

General Approach. The following descriptive statistics will be used: number of observations, mean, standard deviation, median, minimum and maximum for continuous variables; frequencies and proportions for categorical variables; number of events and rates for count variables. Results will be reported in accordance with the extended CONSORT guidelines for pragmatic clinical trials⁶¹ using two-sided statistical tests and confidences intervals. For all analyses, the overall level of significance will be set at 0.05. Methods for multiple comparisons such as Bonferroni, false discovery, or others, will be implemented to maintain the overall 0.05 level of significance. All analyses will be adjusted for site and the presence or absence of opioid use using the criteria provided in **Section 5.3**. All analyses will be performed using SAS v9.4 (SAS Institute, Cary, NC) or the latest version of R (currently 3.6.1; <https://cran.r-project.org/>).

Baseline Descriptive Statistics. Randomization adequacy will be assessed by comparing the distributions of baseline demographic and clinical characteristics between the PCST and Usual Care groups. Comparability for continuous variables will be examined graphically and by summary statistics: mean, standard deviation, median, minimum, and maximum for continuous variables, and frequency and proportion for categorical variables. If statistically and/or clinically meaningful differences are found in baseline characteristics (i.e., baseline characteristics are not balanced between the PCST and Usual Care groups), sensitivity analyses will be conducted with covariate adjustment.

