10.2.2.3. Missing Data

If missing data are unavoidable, they will be addressed by 1) using models that are valid under the missing at random assumption, and 2) performing sensitivity analyses. The generalized linear mixed effects models are valid under the missing at random assumption. The extent and patterns of missing data will be examined, and logistic regression models will be used to identify factors associated with the missingness. Several approaches will be conducted to address the missingness. First, the generalized linear mixed effects models will further adjust for the identified factors associated with the missingness, compensating for potential violation of the missing at random assumption. Second, the propensity of the missingness, calculated from the above logistic regression, can be used to create inverse weighting in the generalized linear mixed effects models. Sensitivity analyses under missing not at random assumptions (e.g. pattern mixture models) will be conducted to examine the robustness of model-based results.⁶³ For time to event analyses, competing risk models such as cause-specific hazards models or sub-distribution hazards models will be used when there are competing events (e.g., death).

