10.6. Populations for Analyses

For questions related to the Phase 1 intervention, analyses will use an intent-to-treat (ITT) approach, in which all available data on all randomized participants are included. Participants who discontinue an assigned intervention will be encouraged to remain in the trial to provide complete follow-up data and will be included in the ITT analysis. For participants with missing outcome ascertainment due to withdrawal or other reasons, data from earlier assessments will be used. For example, for the primary objective for Phase 1, if Week 12 outcome data are not available, baseline data will be used.

The characteristics at the time of randomization for those participants without complete follow-up will be examined; however, there will be limited statistical power to detect differences between participants with and without complete follow-up. To assess potential biases introduced by differential withdrawal among the intervention groups, comparisons of withdrawal rates and/or time to withdrawal will be performed as an ancillary analysis to the primary efficacy analysis.

Other populations that may be used in secondary analyses are defined as follows:

- As-treated population: Any participant randomized into the study regardless of whether they received study intervention. As-treated participants will be analyzed according to the study intervention actually received.

- All-treated population: Any participant randomized into the study that received at least some of the study intervention.
- Per-protocol population: Any participant who was appropriately randomized and was exposed to the protocol-dictated study intervention for $\geq 75\%$ of the planned duration and had the outcome assessments through Week 24.

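### The primary two-visit model yields the raw difference in mean change when both visits are present or baseline is carried forward, so its covariates cannot move the estimate and precision from baseline BPI is unused

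*Combined protocol and SAP*

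**What the plan says.** Section 10.2.2.1 stacks the Week 0 and Week 12 BPI Interference scores as the response: "The linear mixed effects model will include fixed effects of intervention, time, and interactions between intervention and time". The equation has a free arm effect (beta1), a Week 12 effect (beta2), arm by Week 12 (beta3), W as a main effect, and random intercepts for site and participant. W "is a vector of baseline measures, including the stratification factors"; nothing else in it is named. The target is beta3: "The primary efficacy estimand is the contrast of PCST and Usual Care for the change at the 12-week time point".

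Two rules cover a missing Week 12 score. Section 10.2.2.3 relies on the model: "The generalized linear mixed effects models are valid under the missing at random assumption". It adds that "the generalized linear mixed effects models will further adjust for the identified factors associated with the missingness". Section 10.6 says that "if Week 12 outcome data are not available, baseline data will be used". The plan does not say which is primary.

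For baseline imbalance, Section 10.2.2 offers only that "sensitivity analyses will be conducted with covariate adjustment", with no model form. On sample size, Section 10.2.1 says: "All calculations are based on two-sample t tests". Nowhere in Section 10 is Week 12 BPI, or its change, regressed on baseline BPI. There is no W-by-time term, and the arms are not held to a common baseline mean.

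**The concern.** The plan presents this as an adjusted analysis. With two visits and a free baseline arm effect, however, anything constant over time drops out of beta3. Three consequences follow:

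- **Adjustment without effect.** When pairs are complete or baseline is carried forward, adding prognostic baseline variables to W, including baseline BPI, leaves the estimate unchanged. An imbalance analysis run through W as main effects would return the primary estimate again.
- **Unused precision.** Subtracting baseline fixes its slope at 1. Estimating the slope is normally more efficient. This affects the primary endpoint and the continuous secondary outcomes, which follow similar methods.
- **An open definition of W.** If baseline BPI were placed in W while also being a response, the reported standard error would be too small.

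**Working it through.** **1. The plan's own figure.** Inputs from Section 10.2.1: 320 per arm, 20% attrition, interim inflation 1.173, two-sided 5%, 90% power.

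- n per arm = 320 × 0.8 / 1.173 = 218.2
- Detectable difference = SD × (1.960 + 1.282) × sqrt(2/218.2) = 0.621 (SD 2) and 0.931 (SD 3)

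Table 10.2, row 2, gives 0.62 and 0.93. Sizing therefore uses the variance of change, which is also the variance beta3 has.

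**2. Algebra.** Within a participant, Week 12 minus Week 0 = beta2 + beta3·X + (e2 − e1). W, site and participant terms cancel. In the participant's sum the coefficient of X is 2·beta1 + beta3. Because beta1 is free, the sum carries no information on beta3.

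**3. Numerical check.** I fitted the model to one simulated trial with 14 unequal sites, using W = none, opioid use + age, and opioid use + age + baseline BPI.

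- Complete pairs: beta3 = −0.6408 for all three; raw difference −0.6408.
- Baseline carried forward: −0.5800 for all three; raw difference −0.5800.
- Missing Week 12 rows left to the likelihood: −0.564, −0.585, −0.611. Only here does W matter.

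In 2,500 simulated trials per setting, the discrepancy in the first two cases stayed below 1e-13.

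**4. Precision forgone.** Let s0 and s1 be the SDs at baseline and Week 12, and rho their correlation.

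- Var(change) = s0² + s1² − 2·rho·s0·s1
- Residual variance after regression on baseline = s1²(1 − rho²)
- Fractional saving = (s0 − rho·s1)² / Var(change)

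The documents give none of these inputs, so the values below are assumptions (complete pairs):

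| s0/s1 | rho 0.4 | 0.5 | 0.6 | 0.7 |
|---|---|---|---|---|
| 1.0 | 30% | 25% | 20% | 15% |
| 0.9 | 23% | 18% | 12% | 7% |
| 0.8 | 16% | 11% | 6% | 2% |

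The saving is zero when rho equals s0/s1. With 20% baseline carry-forward and zero mean change, each entry is multiplied by 0.8. Simulation at rho 0.5 (8,000 null trials per ratio 1/0.9/0.8) gave 25/18/11% with complete pairs, 20/15/9% with carry-forward and 21/15/9% with the likelihood fit.

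**5. Effect of the entry rule.** Entry at PEG ≥ 4 (Section 5.1) can narrow baseline spread. I assumed a PEG to baseline BPI correlation of 0.6-0.9, screening PEG mean 4-6 and SD 2.5, pre-selection rho 0.5-0.7 with equal SDs, and PEG related to Week 12 BPI only through baseline BPI. The SD ratio becomes 0.75-0.96 and the saving 8-22%.

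**6. On the plan's scale.** The detectable difference shrinks by sqrt(1 − saving): sqrt(0.92) = 0.96 to sqrt(0.78) = 0.88. So 0.62 becomes 0.55-0.60 and 0.93 becomes 0.82-0.89.

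**7. Baseline BPI in W.** With complete pairs and equal SDs, beta3 is unchanged but its reported variance is multiplied by (3 + rho)/4. At rho 0.5 the mean SE falls from 0.198 to 0.185. Two-sided type I error in 8,000 null trials, at SD ratio 1/0.9/0.8:

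- Planned model: 5.1/5.2/5.1% (complete), 5.2/5.5/5.5% (likelihood, 20% missing)
- Baseline BPI added to W: 6.6/6.2/5.7% (complete), 6.6/5.9/5.4% (carry-forward), 9.5/9.1/8.3% (likelihood)

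**The case against.** The strongest reply is that this is a preference about efficiency. The null hypothesis, sizing and analysis all concern change, so the plan is coherent. The gain depends on quantities nobody has stated and may be negligible. All of that stands, and it is why the point concerns precision and specification, not validity.

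Several narrower points also have force:

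- The 8-22% range is a scenario and not a bound. If PEG correlates 0.6 with both visits, the other inputs give 18-32%.
- Equal visit SDs with rho 0.5-0.7 and a change SD of 3 imply visit SDs of 3.0-3.9. That is wide for a 0-10 scale, where a uniform distribution has SD 2.9. The change SD 2 line is the more plausible one.
- Section 10.2.2.3 already plans adjustment for predictors of missingness, and under the likelihood fit this can work. In a simulated pattern where a covariate drives missingness in opposite directions in the two arms, the planned model with that covariate in W recovered the true −0.62 when the covariate acted equally at both visits. It gave about −0.78 when the baseline effect was roughly half. ANCOVA also needs the covariate: about −0.79 without it, −0.62 with it.
- Baseline BPI in W is a possible reading, not a stated plan.
- The beta_4 named in Section 10.2.3 may be the Question 2 model's arm-by-Week-12 coefficient and not a slip for beta3. With missing data the two need not agree, so the text needs clarifying either way.

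None of this alters the identity or the case for using the baseline score.

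**Conclusion.** The concern holds. With complete pairs or baseline carried forward, beta3 is exactly the raw difference in mean change and main-effect W cannot move it. With missing Week 12 rows left to the likelihood, the identity is only approximate and W has some influence. There is no bias under randomization, and the stated power stands. The loss is precision: 30% to 2% of variance across the assumed grid, zero at one limit, and 8-22% in the entry-rule scenario. No specified analysis makes a working adjustment for chance imbalance in baseline BPI beyond subtracting it. W and the primary missing-data rule are also left open. The sponsor should correct this; it does not invalidate the trial.

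**What to change.** Make the primary Question 1 analysis a common-baseline longitudinal model: equal arm means at Week 0, unstructured within-participant covariance, adjusted for opioid stratum and site. It keeps every randomized participant with any data. ANCOVA of Week 12 BPI on arm, baseline BPI, stratum and site, with a stated missing-data rule, is an acceptable alternative. With values missing only at Week 12 and the same covariates, the two agree (largest difference 5e-7 in 20 simulated trials).

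In addition:

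- Do not simply drop beta1 while keeping only a random intercept: simulated type I error was 5.3/6.4/7.6% at SD ratio 1/0.9/0.8. Do not put baseline BPI in W while it is also a response.
- List the contents of W, and reconcile Sections 10.2.2.3 and 10.6. One option is missing at random as primary, with predictors of missingness in the Week 12 regression, and carry-forward and pattern-mixture analyses as sensitivity analyses.
- Specify the imbalance analysis with covariate-by-time terms or as covariates in the Week 12 regression.
- Apply the same approach to Questions 2-3 and the continuous secondary outcomes.
- In Section 10.2.3, name the test statistic as the primary model's arm-by-Week-12 coefficient.
- Keep the planned change contrast as a sensitivity analysis.

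This needs no new data but does amend the primary analysis, so it should be decided blinded to arm results. The documents do not say whether the 50% look took place. The February 2023 log entry about the 640th randomization suggests it was already due, since that look is triggered when participant 320 completes Week 12. If it was taken, record that it used the planned statistic. With the Table 10.3 efficacy bounds (−2.89, −1.97) and futility treated as non-binding, the correlation between an interim change statistic and a final ANCOVA statistic is sqrt(0.5 × (1 − saving)). One-sided type I error then moves from 2.51% to 2.52/2.53/2.55% at savings of 10/20/30%, so switching costs almost nothing in error control.

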4. STUDY DESIGN AND OUTCOMES

4.1. Trial Design and Rationale

The primary trial hypothesis is that pain coping skills training will improve pain and opioid use outcomes more than usual clinical care. The design is a multicenter, sequential, multiple assignment trial with a randomized component (Phase 1) and a non-randomized component (Phase 2). In Phase 1 (Weeks 1 - 24), participants will be randomized into one of two treatment groups: 1. Pain Coping Skills Training (PCST) for 24 weeks, or 2. Usual Care. The PCST intervention has two sequential components each taking place over 12 weeks: 1) weekly telehealth sessions with a PCST coach, and 2) daily interactive voice response (IVR) sessions via telephone. The primary outcome of pain interference will be ascertained at Week 12 which coincides with the end of the PCST weekly coaching sessions. In Phase 2, beginning at Week 24, participants in both randomized groups will be assessed for eligibility for a second intervention, buprenorphine, as an alternative to full agonist opioid pain medication. The main eligibility criterion for the buprenorphine intervention is current use of prescribed opioids at an average dose of \geq 20 morphine milligram equivalents (MME)/day. Participants who meet the buprenorphine eligibility criteria will be encouraged, but not required, to switch from their current opioid medication to buprenorphine to explore buprenorphine as an approach to addressing physical opioid dependence in patients receiving maintenance hemodialysis. Participants who do not meet the buprenorphine eligibility criteria will not be offered buprenorphine. All participants will continue to be followed from Week 24 until Week 36 (Phase 2) for ascertainment of pain, opioid use, and other outcomes to address durability of the effects of PCST, and, for those who switched to buprenorphine, to assess buprenorphine acceptability, tolerability, and efficacy as exploratory outcomes.

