10.2.1.1. Rationale for the Selected Sample Size

The trial will aim to enroll 640 participants. Based on the minimum detectable differences in changes of BPI Interference scores under a range of assumptions provided in **Table 10.2**, for the primary objective of comparing PCST with Usual Care in Phase 1, this sample size will allow detection of a difference in the change in BPI Interference score of 0.62 if there is no intra-cluster correlation and a standard deviation of change of 2, or 1.17, under the conservative assumptions of an intra-cluster correlation coefficient (ICC) of 0.02 and a standard deviation of change of 3 (which is larger than the SD of change observed in studies of chronic pain in non-ESRD patient populations⁵⁷). Based on a review of the literature, the Initiative on Methods, Measurement, and Pain Assessment in Clinical Trials identified 1 as the minimal clinically important change *for individuals* on the BPI Interference scale.⁵⁷ However, this group also recognized a critical tenet of randomized trials with between group comparisons: "...criteria for clinically important change in individuals cannot be directly applied to the evaluation of clinically important group differences." Determination of the importance of group differences must be established in the broader context of the disease being treated, the currently available treatments, and the overall risk-benefit evaluation of the treatment. Our proposed sample size will allow us to detect a between-group difference *as small as* the ranges listed above. We hypothesize that the actual observed difference will be larger because we are testing an adaptation of an evidence-based intervention that has had moderate effect sizes in other populations and settings.²⁷⁻²⁹

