10.2.3.2 Analyses of the Secondary Endpoints

The secondary endpoints include pain severity, pain catastrophizing, opioid use, other PROs, hospitalizations, falls and mortality.

For continuous endpoints, such as pain severity, pain catastrophizing, and opioid use expressed as MME/day., similar methods as described for the primary outcome will be used to compare differences in changes of the endpoints between PCST and Usual Care at 12 (**Table 10.1; Question 1**), 24 (**Table 10.1; Question 2**), and 36 (**Table 10.1; Question 3**) weeks; i.e., linear mixed effects models with adjustment for baseline measures (and additional adjustment for buprenorphine eligibility and initiation of buprenorphine for **Question 3 in Table 10.1**), taking into account the repeated measures over time and clustering of recruitment sites via random effects.

For binary endpoints, such as the composite of pain interference and opioid use, generalized linear mixed effects models with a binomial distribution and a log link adjusting for baseline measures (additionally adjusting for buprenorphine eligibility and initiation of buprenorphine for **Question 3 in Table 10.1**), taking into account the repeated measures over time and clustering of recruitment sites via random effects, will be used to compare relative risks between PCST and Usual Care at 12 (**Table 10.1; Question 1**), 24 (**Table 10.1; Question 2**), and 36 (**Table 10.1; Question 3**) weeks.

For recurrent endpoints (counts) such as number of hospitalizations and falls, participants will be followed from baseline to 36 weeks, loss-to-follow-up, or death, whichever comes first. Generalized linear mixed effects models with a Poisson distribution, an offset of follow-up time and a log link adjusting for baseline measures (additionally adjusting for buprenorphine eligibility and initiation of buprenorphine for **Question 3 in Table 10.1**) will be used to compare event rates between PCST and Usual Care during the Phase 1 study period (**Table 10.1; Questions 1 – 3**). Repeated measures over time and clustering of recruitment sites will be taken into account via random effects.

For time to event endpoints such as mortality, participants will be followed from baseline to 36 weeks, loss-to-follow-up, or death, whichever comes first. Cox proportional hazards models will be used to compare risks of

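### The Week 24 and Week 36 models handle within-participant correlation only through a random intercept, so their standard errors will be too small if correlation falls with time

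*Combined protocol and SAP*

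**What the plan says.** Section 10.2.2.1 writes the Week 12 primary model with fixed effects for intervention, time and their interaction, "taking into account the repeated measures over time and clustering of recruitment sites via random effects". The equation has one scalar random effect per recruitment site, one scalar random effect per participant, and an error term whose covariance across visits is not described.

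For Question 2 (Week 24) the model gains a third visit. For Question 3 (Week 36) it "is revised by adding the BPI Interference score at 36 weeks to the dependent variable", which makes four visits. Only fixed effects are added: visit and treatment-by-visit terms, plus buprenorphine eligibility and initiation for Question 3. The random part does not change. The only model diagnostic named is for normality.

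For continuous secondary outcomes at Weeks 12, 24 and 36, the section headed 10.2.3.2 says that "similar methods as described for the primary outcome will be used".

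Section 10.2.2 sets the error rate: "For all analyses, the overall level of significance will be set at 0.05", "using two-sided statistical tests and confidences intervals". Table 10.1 labels Questions 2 and 3 as secondary.

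**The concern.** A participant random intercept with independent, constant-variance errors implies one variance for the change between any two visits. With two visits that does no harm, because there is only one change to estimate. With three or four visits the model averages over all pairs and applies the average to each contrast.

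The reported contrasts, baseline to Week 24 in Question 2 and baseline to Week 36 in Question 3, are each the longest interval in their model. If scores further apart in time correlate less, the true variance of that change exceeds the average. The standard error is then too small, the interval too narrow and the p-value too low. Multiplicity adjustment does not repair this, because it starts from the same p-values.

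At stake are the conclusions on coaching plus IVR at 24 weeks and on durability at 36 weeks. The Week 24 and Week 36 contrasts of continuous secondary outcomes measured at three or more visits are exposed in the same way.

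**Working it through.** **Planning figures reproduced first.** The plan gives precision for Week 12 only: "for a power of 90%, a type 1 error of 5%, an attrition rate of 20%, standard deviations of change of 2 and 3" (Section 10.2.1). "The trial will aim to enroll 640 participants" (Section 10.2.1.1), and (80 × 8)/2 in the plan's own formula implies 320 per arm. With design effect 1.574 and interim inflation 1.173:

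- n per arm = 320/1.574 × 0.8/1.173 = 138.7 (plan: 139).
- Detectable difference = SD × (1.960 + 1.282) × √(2/138.7) = 0.78 for SD 2 and 1.17 for SD 3 (plan: 0.78 and 1.17).
- With ICC 0, n = 320 × 0.8/1.173 = 218.2, giving 0.62 and 0.93 (plan: the same).

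The plan states no standard error or detectable difference for Week 24 or Week 36.

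**Inputs for the check.** The visits (0, 12, 24 and 0, 12, 24, 36) and the random effects come from Section 10.2.2.1. Between-visit correlations and visit SDs are not in the documents, so those below are assumptions.

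**Formulas (complete data, T visits, true within-participant covariance V).**

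- Residual variance under the random-intercept model: s² = [trace(V) − sum(V)/T]/(T − 1).
- Variance of change implied by the model: 2s², for every pair of visits.
- True variance of change from baseline to visit k: V00 + Vkk − 2V0k.
- SE ratio = √(2s²/true). Type I error = 2 × [1 − Φ(1.96 × ratio)].

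The site intercept cancels from within-participant change. The Question 3 buprenorphine terms are left out.

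**Two visits.** 2s² equals V00 + V11 − 2V01 exactly, so the ratio is 1.00 whatever the SDs. The Week 12 primary contrast is unaffected.

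**One case in full.** Take correlations 0.6/0.5/0.4 at 12/24/36 weeks apart, unit variances and four visits. The six pairs average (3 × 0.6 + 2 × 0.5 + 0.4)/6 = 0.533, so s² = 0.467 and 2s² = 0.933. The true Week 36 variance is 2 × (1 − 0.4) = 1.200. The ratio is √(0.933/1.200) = 0.88, and the type I error is 8.4%.

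**Equal SDs (unit variances).**

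| Correlations at 12/24/36 weeks | Week 24: model, true | SE ratio, type I | Week 36: model, true | SE ratio, type I |
|---|---|---|---|---|
| 0.60/0.55/0.50 | 0.833, 0.900 | 0.96, 5.9% | 0.867, 1.000 | 0.93, 6.8% |
| 0.60/0.50/0.40 | 0.867, 1.000 | 0.93, 6.8% | 0.933, 1.200 | 0.88, 8.4% |
| 0.65/0.55/0.45 | 0.767, 0.900 | 0.92, 7.1% | 0.833, 1.100 | 0.87, 8.8% |
| 0.7 per step (0.70/0.49/0.343) | 0.740, 1.020 | 0.85, 9.5% | 0.859, 1.314 | 0.81, 11.3% |
| 0.60 throughout | 0.800, 0.800 | 1.00, 5.0% | 0.800, 0.800 | 1.00, 5.0% |

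**Smaller baseline SD (1.8, then 2.4 at each later visit), same formulas.**

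| Correlations | Week 24: ratio, type I | Week 36: ratio, type I |
|---|---|---|
| 0.60/0.55/0.50 | 0.997, 5.1% | 0.983, 5.4% |
| 0.60/0.50/0.40 | 0.966, 5.8% | 0.934, 6.7% |
| 0.60 throughout | 1.03, 4.3% | 1.05, 4.0% |

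**With dropout.** A simulation used 640 participants, 1,500 runs per case and assumed cumulative dropout of 20%/25%/28%. At 0.7 per step the type I error was 10.3% (Week 24) and 11.1% (Week 36). At 0.65/0.55/0.45 it was 7.4% and 8.9%. At equal correlation 0.6 it was 5.5% and 5.0%. Monte Carlo error is about 0.6-0.8 points. Dropout does not change the picture.

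**The case against.** The strongest reply is that nothing in the documents shows that the standard errors will in fact be wrong. They give no between-visit correlations or visit SDs, and the error covariance is left unstated rather than declared independent. Under equal correlation and equal SDs the model is exactly right. Entry requires a PEG score of at least 4, which could narrow the baseline spread, and a smaller baseline SD offsets part or all of the shortfall. That stands: the point is conditional, and its direction depends on which departure dominates.

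A reader might infer that every continuous secondary outcome is affected. The documents do not support that. Week 12 contrasts under Question 1 come from two visits, and the Everyday Discrimination Scale is collected only at Weeks 0 and 36.

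It is also fair that Questions 2 and 3 are secondary and that robust standard errors would be another remedy.

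The gap itself remains. The plan names no random slope, other covariance structure, robust standard error or covariance check. The design gives little reason to expect equal correlation: the BPI looks back 7 days, visits are 12 weeks apart, delivery changes from coaching to IVR after Week 12, and some participants switch to buprenorphine after Week 24.

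**Conclusion.** The concern holds as a conditional risk to secondary analyses. If correlation declines with time, from 0.60/0.55/0.50 to 0.7 per 12-week step with equal SDs and complete data, the standard errors are too small by about 4-15% at Week 24 (type I error about 6-9.5%) and 7-19% at Week 36 (about 7-11%). The error is nil with equal correlation and equal SDs, and smaller when the baseline SD is smaller. With equal correlation 0.6 and SDs of 1.8 v 2.4, standard errors are about 3-5% too large. The documents cannot place the trial within this range.

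A reader might conclude that the Week 24 and Week 36 p-values are wrong as planned, or that the primary result is compromised. Neither follows. The first needs correlations that the documents do not give. The second fails because the two-visit Week 12 contrast has the correct standard error under this model, and the interim analysis in Section 10.2.3 tests that same Week 12 objective.

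**What to change.** For Questions 2 and 3, and for the Week 24 and Week 36 contrasts of continuous secondary outcomes with three or more visits, replace the participant random intercept with an unstructured within-participant covariance. Fit it by REML with Kenward-Roger degrees of freedom and keep the site random effect. Pre-specify the fallback: if the model does not converge, keep the random intercept and use robust (sandwich) standard errors. The Week 12 primary model needs no change.

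The cost is SAP wording. The within-participant part then has 6 covariance parameters (three visits) or 10 (four visits) in place of 2, which is negligible with 640 participants. If correlation and SDs do turn out equal, almost nothing is lost.
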